# 6.3.2 In case of Anemia

In case of grade  $\geq$  2 severity anemia, the Investigator will instruct the subject to interrupt IMP administration and to return to the study center within 7 days to perform a re-test of absolute reticulocyte count.

If the re-test value is below 50% of baseline, and/or if an alternative cause for the anemia cannot be documented, treatment will not be resumed. IMP administration will be resumed only if the re-test value for the absolute reticulocyte count is  $\geq$  50% of the baseline value and an alternative cause for the anemia can be documented. The subject will continue to be closely monitored until normalization, i.e. return to baseline values.

Protocol No.: GSN000300	Compound No.: GKT137831
Protocol Version No.: Final 4.0; Amendment 3	Sponsor: Genkyotex
Protocol Date: 24 July 2018	Author: Cmed Clinical Services

Withdrawals will be handled as described in Section 5.6.5.

# 6.3.3 In case of Drug Induced Hypothyroidism

In case of TSH  $\geq$  10 mIU/L, the Investigator will instruct the subject to interrupt IMP administration and to return to the study center within 2-3 days to perform a re-test of TSH and measure free T4.

If the re-test value is  $\geq$  10 mIU/L and the subject presents with signs and symptoms consistent with hypothyroidism or if overt biological hypothyroidism is confirmed (i.e. TSH  $\geq$  10 mIU/L and reduced free T4), treatment will not be resumed. If drug induced hypothyroidism is not confirmed, IMP administration will be resumed as per protocol. The subject will continue to be closely monitored until normalization, i.e. return to baseline values.

Withdrawals will be handled as described in Section 5.6.5.

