# 5.3 Exclusion Criteria

A potential subject who meets any of the following criteria will be excluded from participation in this study:

- 1. A positive pregnancy test or breast-feeding for female subjects.
- 2. Any hepatic decompensation, defined as a past or current history of hepatic encephalopathy, gastrointestinal tract bleeding due to esophageal varices, or ascites.
- 3. INR > 1.2 unless subject is on anticoagulant therapy.
- 4. ALT > 3 x ULN.
- 5. Total bilirubin > 1 x ULN.
- 6. Planned or current plasmapheresis or other extra-corporeal treatments (e.g., MARS) for treatment-refractory pruritus.
- History of liver transplantation, current placement on a liver transplant list or current MELD score
  ≥ 15.
- 8. Cirrhosis with complications, including history or presence of: spontaneous bacterial peritonitis, hepatocellular carcinoma.
- 9. Hepatorenal syndrome (type I or II) or Screening serum creatinine > ULN.
- 10. Competing etiology for liver disease (e.g., hepatitis C, active hepatitis B, NASH, ALD, autoimmune hepatitis, primary sclerosing cholangitis, Gilbert's Syndrome).
- 11. Subjects receiving prohibited medications within 3 months of Screening (Visit 1) according to the list (a, b and c) provided in Section 6.6.2.
- 12. Treatment with any investigational agent within 4 weeks of Screening (Visit 1) or 5 half-lives of the IMP (whichever is longer).
- 13. A history of long QT syndrome.
- 14. Evidence of any of the following cardiac conduction abnormalities during the screening period:
  - A QTc Fredericia interval > 450 milliseconds for males and > 470 milliseconds for females.
  - A second or third degree atrioventricular block not successfully treated with a pacemaker.
- 15. A history of severe cardiovascular disease defined as any of the following within the 12 weeks preceding initiation of study treatment:
  - Acute myocardial infarction or unstable angina pectoris.

- A coronary revascularization procedure.
- Congestive heart failure New York Health Association (NYHA) Class III or IV.
- Stroke, including a transient ischemic attack.
- 16. History of cancer in the preceding 5 years, except adequately treated non-melanoma skin cancer, carcinoma *in situ* of the cervix, *in situ* prostate cancer, *in situ* breast ductal carcinoma, or superficial bladder cancer stage 0).
- 17. The occurrence of any acute infection requiring systemic antibiotic therapy within 2 weeks prior to Screening (Visit 1), or HIV infection.

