# 7.2 Enrollment/Baseline

## Visit 2 (Day 1)

The following assessments and procedures will be performed at baseline:

- Confirmation of eligibility (not every eligibility assessment needs to be repeated; i.e., confirmatory laboratory and diagnostic tests. Subjects with AEs at baseline may need to be withdrawn in accordance with the eligibility and withdrawal criteria).
- Body weight.
- Urine pregnancy test for female subjects of childbearing potential.
- Optional collection of blood sample for DNA (only for subjects who have signed the additional, specific consent form).
- Blood samples for markers of inflammation and liver injury (hsCRP, fibrinogen, IL-6, CK-18).
- Blood samples for markers of fibrosis (ELF score, collagen fragments).
- Blood samples for optional assessments of immunological markers (IgM, IL-4, IL-12, IL-17A, IFNγ).
- Blood samples for mandatory and optional assessments of bile acid metabolism (serum, C4, total bile acids, FGF-19).
- Blood samples for optional additional biomarkers.
- Blood samples for optional metabolomic studies.
- Transient elastography (FibroScan® or similar technology).
- Safety hematology and biochemistry including blood lipids, triglycerides, liver function tests and INR.
- Thyroid function tests.
- PBC-40 QoL questionnaire and pruritus VAS.
- Pulse rate, SBP and DBP.
- Symptoms-directed physical examination.
- Concomitant medication recording.
- Randomization.
- Dispense IMP.
- Supervise subject during first self-administration of IMP.
- Recording of AEs.

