# 8.2 Laboratory Evaluations

# 8.2.1 Clinical Laboratory Evaluations

The following safety laboratory investigations will be conducted at time points indicated in "Schedule of Assessments" (Appendix A).

The following clinical safety laboratory tests will be performed at each visit:

- Hematology: hematocrit, hemoglobin, absolute and relative reticulocyte counts, red blood cell (RBC) count, white blood cell (WBC) count, differential WBC count, platelet count, absolute neutrophil count, mean cell volume and INR.
- Biochemistry: glucose, total protein, albumin, creatinine, urea, creatine kinase, total cholesterol, triglycerides, sodium, potassium, chloride, ALP, AST, ALT, conjugated and total bilirubin and GGT.
- TSH levels will be tested at each visit, except Visits 1 and 8. Free T4 will be also measured if TSH levels are ≥ 10 mIU/L.

Urinalysis (to be performed at Visits 1, 5, 7 and 8): quantitative test for pH and protein; qualitative tests for glucose, ketones, bilirubin, blood; microscopic examination of the sediment.

Viral serology will be performed at Screening (Visit 1): HIV antibodies (1 and 2), hepatitis B surface antigen and hepatitis C virus antibodies.

Determination of AMA will be performed at Screening (Visit 1): AMA titer, or if AMA is negative or in low titer (<1:80) PBC specific antibodies (anti-GP210 and/or anti-SP100 and/or antibodies against the major M2 components [PDC-E2, 2-oxo-glutaric acid dehydrogenase complex]).

Female subjects of child-bearing potential must have a negative serum pregnancy test documented at Screening (Visit 1). A negative urine pregnancy test must be done prior to study intervention at baseline/Day 1 (Visit 2) and all subsequent visits and the results must be available prior to dispensing of IMP.

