### 14.1 Data Capture Methods

Clinical data (including AEs, concomitant medications, safety assessments and outcome measures) will be entered by the site staff into a 21 CFR Part 11-compliant data capture system provided by Cmed. Clinical laboratory data will be entered by a central laboratory, with reports provided electronically to the sites for their records and to Cmed for loading into the database. The data capture system includes password protection and internal quality checks, such as automatic range checks, to identify data appearing inconsistent, incomplete or inaccurate.

CRO personnel will be responsible for training of investigator-designated site staff on the correct use of the EDC system. Authorized study staff will only be given access once they have received training.

Subjects will be provided with separate paper-based PBC-40 questionnaires and pruritus VAS at baseline/Day 1 and Weeks 12 and 24 (Visits 2, 5 and 7, respectively). Authorized site staff will then enter the responses provided in the eCRF with the original questionnaires being retained as part of the source documents.

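### TSH is first drawn at the Day 1 dosing visit and no entry criterion limits it, so a subject can be randomized and dosed while already at the TSH interruption level

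*Protocol*

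**What the plan says.** **Trigger and stop.** Under Protocol 6.3.3, a TSH of 10 mIU/L or more leads the investigator to "instruct the subject to interrupt IMP administration and to return to the study center within 2-3 days to perform a re-test of TSH" and to measure free T4. Treatment is not resumed if the re-test is again ≥ 10 with hypothyroid signs and symptoms, "or if overt biological hypothyroidism is confirmed" (TSH ≥ 10 with reduced free T4). If drug-induced hypothyroidism is not confirmed, IMP resumes. Neither the trigger nor the stop refers to the subject's baseline TSH.

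**Sampling.** Protocol 8.2.1: "TSH levels will be tested at each visit, except Visits 1 and 8". The Screening list in 7.1 has no thyroid test, and Appendix A marks thyroid tests from Day 1 to Week 24. The endpoint table in Section 3 lists fewer TSH visits but also starts at Day 1.

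**Day 1.** Visit 2 (Protocol 7.2) contains the first thyroid sample, randomization, dispensing and "Supervise subject during first self-administration of IMP". On eligibility it says "not every eligibility assessment needs to be repeated; i.e., confirmatory laboratory and diagnostic tests". Protocol 14.1: "Clinical laboratory data will be entered by a central laboratory, with reports provided electronically to the sites for their records". No step makes randomization or dosing wait for the TSH result.

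**Entry limits.** Protocol 5.3 excludes ALT above 3 x ULN, "Total bilirubin > 1 x ULN" and "INR > 1.2 unless subject is on anticoagulant therapy". None of the 8 inclusion or 20 exclusion criteria names TSH.

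**The concern.** Protocol 2.1.1 says that auto-immune thyroid disease often accompanies PBC, and 2.1.4 lists effects on thyroid hormones among the treatment-related findings in dogs. Even so, thyroid status is unknown when the first dose is taken. A subject already at TSH ≥ 10 mIU/L is dosed, then held once the Day 1 or Week 2 value is reported. Because TSH is drawn at every visit to Week 24, a persistently raised value can trigger a hold again and again.

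If that subject is overtly hypothyroid, 6.3.3 stops treatment permanently for a condition that preceded the drug. The section is also hard to apply in this case. One sentence forbids resumption once overt hypothyroidism is confirmed, and the next resumes IMP if *drug-induced* hypothyroidism is not confirmed. Monitoring then runs until values return to baseline, which for this subject is not normal. At stake are exposure before a known safety parameter is checked, an avoidable discontinuation, and usually a lost primary-endpoint value.

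**Working it through.** The plan states no figure on this point, so there is nothing to reproduce.

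**1. Entry limit against trigger (Protocol 5.3 against 6.3.1 to 6.3.3)**

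| Parameter | Entry limit | Interruption trigger | Limit below trigger? |
|---|---|---|---|
| ALT | 3 x ULN | 5 x ULN | Yes |
| Total bilirubin | 1 x ULN | 1.5 x ULN | Yes |
| INR, no anticoagulant | 1.2 | 1.5 x ULN (1.5 to 1.8 for an assumed ULN of 1.0 to 1.2) | Yes |
| INR, anticoagulated | none | 1.5 x ULN | No |
| AST | none | 5 x ULN | No |
| Hemoglobin | 10.0 g/dL | Grade ≥ 2 anemia, cut-off not printed | Cannot be compared |
| TSH | none, not measured at Screening | 10 mIU/L | No |

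**2. How many subjects.** The prevalence of pre-dose TSH ≥ 10 is not in the documents. Assumed range: 1% to 5%; N = 102 (Protocol 10.2).
- Expected number: 0.01 x 102 = 1.0; 0.05 x 102 = 5.1. Per arm of 34: 0.34 to 1.7.
- Chance of at least one: 1 − 0.99^102 = 64%; 1 − 0.95^102 = 99%. These only restate the assumed prevalence.
- Permanent stops, if 20% to 50% have reduced free T4 or symptoms (also assumed): 0.2 x 1.02 = 0.2; 0.5 x 5.1 = 2.6, over all three arms.

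**3. Cost of holds for those who resume.** One hold of 2 to 3 days out of 168 is 1.2% to 1.8% of treatment. Five samples come before the end-of-treatment visit (Day 1 and Weeks 2, 6, 12 and 18). If each one triggers a hold, the loss is 5 x 2 = 10 to 5 x 3 = 15 days, or 6.0% to 8.9%, before any laboratory turnaround.

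**4. Last GGT sample after a permanent stop.** Inputs: re-test within 3 days (6.3.3); follow-up within 28 days of the early termination visit (5.6.5, 7.5); ± 3 days at Week 2 and at follow-up (7.3, 7.4); Week 12 window opening on day 64 (SAP 6.4). The early termination visit is taken to fall on the re-test day.
- Stop on the Day 1 value: 0 + 3 + 28 + 3 = day 34, which is 64 − 34 = 30 days short of the window.
- Stop on the Week 2 value: 14 + 3 + 3 + 28 + 3 = day 51, which is 64 − 51 = 13 days short.

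SAP 6.2 carries forward only values from the Week 12 visit or later. Unless turnaround and scheduling add 30 or 13 days, no Week 24 value is imputed. Protocol 10.4.3.7 speaks of imputing for all subjects, but SAP 6.2 is the rule that says how.

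**5. Power, as an upper bound.** Inputs: difference 28, SDs 30 and 40, two-sided alpha 0.023475 (Protocol 10.2). Method: noncentral t with each arm's n multiplied by the Wilcoxon efficiency of 0.955. At 34 per arm, power is 80.5%, in line with the planned 80%. At 33 per arm it is 79.2%. One subject lost per arm is three in total, more than the 2.6 in step 2, so about 1.4 points slightly overstates the worst case under these assumptions.

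**The case against.** **The human data are reassuring.** Thyroid hormones were specifically studied in the multiple ascending dose study, and mean values stayed in the normal range without a trend (2.1.5.1). The phase 2 study showed no thyroid signal (2.1.5.2, 2.2, 2.3). The dog finding is given without direction. This stands. A reader might infer that brief exposure would harm a hypothyroid subject; the documents do not say so. Phase 2 did, however, stop at 200 mg BID for its last 6 weeks, against up to 400 mg BID for 24 weeks here, and the sponsor judged a thyroid stopping rule necessary.

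**Existing criteria give some cover.** Exclusion 20 lets the investigator exclude known uncontrolled disease. Exclusion 11, through 6.6.2(c), bars users of liothyronine and liotrix. That is partial cover: the list does not name levothyroxine, and neither criterion detects disease that nobody has measured.

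**Frequency is unsupported.** Protocol 2.1.1 speaks of co-diagnosed, hence recognized, thyroid disease. It gives no rate of unrecognized TSH ≥ 10. This stands, and the number affected cannot be sized from the documents.

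**TSH is not the only gap.** A reader might infer that every other trigger is absolute and protected at entry. That is not so: AST and INR in anticoagulated subjects have no entry limit. Nor is the Grade ≥ 2 liver-related AE trigger absolute, because an AE must emerge or worsen relative to baseline (9.2.1).

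**The remedy is wider than the harm.** Subjects with neither symptoms nor reduced free T4 could resume IMP and supply Week 24 data, yet an entry limit would defer or exclude them. This is a real cost, though these subjects may face repeated holds rather than one. A note in 6.3.3 to consider the Day 1 value would help attribution, but only after dosing.

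**Conclusion.** The gap is real: first TSH sample, randomization and first dose share one visit, no entry criterion limits TSH, and the 6.3.3 trigger and stop ignore baseline. Its consequence is small. Under the assumed 1% to 5% prevalence and 20% to 50% overt or symptomatic share, about 1 to 5 subjects would enter at the trigger and 0.2 to 2.6 would be permanently stopped. Subjects who discontinue are not replaced (5.6.5) and the sample size has no dropout allowance (10.2), but the power loss is negligible.

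A reader might infer bias in the GGT comparison or a contaminated thyroid safety analysis. Neither follows. Pre-existing cases should balance across arms by randomization, and the change-from-baseline and shift tables in SAP 8.10.2, with the listings, already separate prior from new abnormalities. The point is a minor safety and coherence improvement, with medium confidence because its size rests on assumed rates.

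**What to change.** 1. Add TSH, with reflex free T4 at ≥ 10 mIU/L, to Visit 1 (Protocol 7.1, 8.2.1, Appendices A and B).
2. Add to 5.3: a subject with Visit 1 TSH ≥ 10 mIU/L is not randomized unless a re-test during screening is < 10 mIU/L.
3. Leave the 6.3.3 trigger and stop unchanged, so that no safety rule is relaxed.

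**Cost.** Appendix B puts the thyroid panel at 2 mL. Visit 1 rises from 21.2 to 23.2 mL and the study total from 241.1 to 243.1 mL (2/241.1 = 0.8%). There is one extra assay per screened subject. Visit 1 falls at Week -4 to -1, which leaves at least a week for the result.

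**Downside.** At the assumed rates, about 1 to 5 otherwise eligible subjects, including subclinical cases who could have resumed IMP, are deferred or excluded in a trial that expects low enrollment (2.2).

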# 6.4 Accountability Procedures for the Study Treatment(s)

Records will be maintained of the delivery of IMP to the study centers, the inventory at the study centers, the allocation to, use of, and return by each subject to the study center, and the return to the Sponsor.

These records will include dates, quantities, batch numbers, expiry dates and the unique code numbers assigned to the IMP and to the study subjects. No subject diary is planned.

The Investigator will be responsible for ensuring the records adequately document that the subjects are provided the doses specified in the protocol and all IMP received from the Sponsor is reconciled.

# 6.5 Subject Compliance

The assigned IMP, dosage, timing and mode of administration may not be changed, except as described in Section 6.3. Any departures from the intended regimen must be recorded in the eCRF.

IMP accountability and subject compliance will be documented throughout the study using studyspecific IMP dispensing and return record forms.

Subjects will be asked to return all used IMP, including empty and partially used containers. IMP will be dispensed at baseline/Day 1 (Visit 2), Week 2 (Visit 3), Week 6 (Visit 4), Week 12 (Visit 5) and Week 18 (Visit 6). At Week 2 (Visit 3), Week 6 (Visit 4), Week 12 (Visit 5), Week 18 (Visit 6) and Week 24 (Visit 7), the unused IMP dispensed to the subject at the previous visit will be returned to the Investigator. The Investigator will determine compliance by capsule count per bottle and batch number. Subjects exhibiting non-compliance as assessed by capsule counts will be counseled on the importance of good compliance to the study dosing regimen. Drug non-compliance is defined as taking less than 80% or more than 120% of IMP during the double-blind treatment period.

# 6.6 Concomitant Medications/Treatments

# 6.6.1 Required Concomitant Medications

Subjects must be taking UDCA for at least 6 months and be on a stable dose (defined as no changes) for at least 3 months prior to the first Screening visit (Visit 1). All efforts should be made to keep the dose of UDCA stable during the treatment period. Changes in UDCA dose during the treatment period will lead to the early discontinuation of the study subject.

# 6.6.2 **Prohibited Medications**

Note: these are not exhaustive lists. The FDA and other agencies maintain current lists, which can be referred to via their websites. Furthermore, these lists will evolve as new drugs come to market and more is learned about the pharmacology of GKT137831 and other medications. Therefore, they should be regarded as a minimum set of excluded and pre-cautioned concomitant medications.

The following medications are prohibited within 3 months of Screening (Visit 1) and during the double-blind treatment period:

- a) OCA, budesonide and other systemic corticosteroids, colchicine, mycophenolate mofetil, azathioprine, sulfasalazine, leflunomide, cyclophosphamide, fenofibrates and other fibrates, valproate, isoniazid, and nitrofurantoin.
- b) Any biologic agent within 12 weeks or 5 half-lives prior to Screening (Visit 1), whichever is longer. In the case of rituximab, use within 168 days (24 weeks) of Screening or no recovery (level < 20% of pre-rituximab levels or below lower level of normal, whichever is lower) of CD19-positive B lymphocytes if the last dose of rituximab has been more than 24 weeks prior to Screening.
- c) Patients taking the following medications which are OAT1 and OAT3 substrates are not allowed on the study because of the underlying conditions these medications are used to treat: methotrexate, probenecid, aminohippurate, cephradine, cidofovir, adefovir, oseltamivir, acyclovir, ganciclovir, benzylpenicillin, cefaclor, ceftizoxime, bumetanide, famotidine, conjugated equine estrogens\*, liothyronine, ouabain, caspofungin, liotrix, romidepsin, fluvastatin, paclitaxel, docetaxel, cobimetinib, selexipag, ambrisentan, grazoprevir, technetium tc 99m mebrofenin, and parachlorophenol. Should these drugs become necessary during the treatment period, the treating physician should make all efforts to use alternative drugs. However, where it is not feasible or desirable to change to an alternative, the subject must be monitored closely for occurrence of adverse events possibly related to drug accumulation as well as clinical effects of increased exposure, and consideration must be given to reducing the dose.

\*Only equine estrogen derivatives are prohibited. Synthetic estradiol is allowed.

In addition, the following medications are prohibited during the double-blind treatment period:

Protocol No.: GSN000300	Compound No.: GKT137831
Protocol Version No.: Final 4.0; Amendment 3	Sponsor: Genkyotex
Protocol Date: 24 July 2018	Author: Cmed Clinical Services

- d) Systemically administered potent CYP3A4 inhibitors: itraconazole, lopinavir/ritonavir, telaprevir, clarithromycin, ritonavir, ketoconazole, indinavir, conivaptan, and voriconazole.
- e) Sensitive CYP3A4 substrates which have a narrow therapeutic range: alfentanyl, astemizole, cisapride, cyclosporine, dihydroergotamine, ergotamine, fentanyl, pimozide, quinidine, systemic sirolimus, systemic tacrolimus, terfenadine. However, should fentanyl or alfentanyl use become necessary during the study, and where it is not feasible or desirable to change to an alternative, use of fentanyl or alfentanyl is permitted provided the dose is carefully titrated.
- f) UGT inhibitors and inducers: atazanavir, rifabutin, carbamazepine, phenytoin, oxcarbazepine, nevirapine, methsuximide and phenobarbital.
- g) Pruritus medication: rifampicin, naltrexone. Anti-histamines are permitted, if the dose is stable for at least 8 weeks before Screening (Visit 1) and throughout the study.

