# 5.2 Inclusion Criteria

In order to be eligible to participate in this study, a subject must meet all of the following criteria:

- 1. Male or female aged 18 to 80 years, inclusive.
- 2. Willing and able to give written informed consent and to comply with the requirements of the study.
- 3. PBC diagnosis as demonstrated by the presence of  $\geq$  2 of the following 3 diagnostic factors:
  - a) History of elevated ALP levels (>ULN) for at least 6 months
  - b) Positive AMA titer or if AMA negative or in low titer (<1:80) PBC specific antibodies (anti-GP210 and/or anti-SP100 and/or antibodies against the major M2 components [PDC-E2, 2-oxo-glutaric acid dehydrogenase complex])

  - c) Liver biopsy consistent with PBC (based on historic liver biopsy), including nonsuppurative, destructive cholangitis affecting mainly the interlobular and septal bile ducts.
- 4. Serum ALP ≥1.5 x ULN.
- 5. Serum GGT ≥1.5 x ULN.
- 6. UDCA treatment for at least 6 months and stable dose for at least 3 months prior to Visit 1.
- 7. Subjects being treated for pruritus with colestyramine must be on a stable dose of colestyramine for at least 8 weeks prior to baseline/Day 1 (Visit 2). Subjects must be willing and able to take colestyramine at least 2 hours before or after study medication.
- 8. Female subjects of childbearing potential must use a highly effective method of contraception to prevent pregnancy for 4 weeks before randomization and must agree to continue strict contraception for 90 days after last administration of IMP (see Section 5.4). Male participants with female partners of childbearing potential must be willing to use a condom and require their partner to use an additional form of adequate contraception as approved by the Investigator.

Protocol No.: GSN000300	Compound No.: GKT137831
Protocol Version No.: Final 4.0; Amendment 3	Sponsor: Genkyotex
Protocol Date: 24 July 2018	Author: Cmed Clinical Services

This requirement begins at the time of informed consent and ends 90 days after the last administration of IMP. Male study participants must also not donate sperm from baseline until 90 days after the last administration of IMP.

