# 7.1 Screening

## Visit 1 (Week -4 to -1)

The following assessments and procedures will be performed at Screening:

- Signed informed consent.
- Determination of eligibility.
- Demographics and medical history.
- Height and oral or tympanic temperature.
- Serum pregnancy test for female subjects of childbearing potential.
- Blood sample for viral serology (HIV antibodies 1 and 2, hepatitis B surface antigen and hepatitis C virus antibodies).
- Blood samples for the determination of anti-mitochondrial antibodies (anti-AMA, anti-GP210, anti-SP100, antibodies against the major M2 components [PDC-E2, 2-oxo-glutaric acid dehydrogenase complex]).
- Safety hematology and biochemistry including blood lipids, triglycerides, liver function tests and INR.
- Urinalysis (dipstick).
- Pulse rate, SBP and DBP.
- 12-lead ECG.
- Complete physical examination.
- Prior and concomitant medication recording.
- Recording of AEs.

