# 8 STUDY PROCEDURES/EVALUATIONS

# 8.1 Clinical Evaluations

# 8.1.1 Demographics and Medical History

Demographic and baseline characteristic data will be collected on all subjects at Screening (Visit 1).

Relevant medical history/baseline medical conditions will be recorded.

Prior and concomitant medications history will be recorded (prescription medications, over-thecounter and herbal remedies). Assessment of eligibility at Visits 1 and 2 should include a review of permitted and prohibited medications (see Section 6.6).

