## Pruritus VAS

Pruritus will be self-assessed by the subject using a Pruritus VAS (see Appendix D) at baseline/Day 1 (Visit 2), Week 12 (Visit 5) and Week 24 (Visit 7). To capture the intensity of itching within the 24 hours preceding these visits, subjects are to be asked to write a number from 0 to 10 below the horizontal scale, with no decimal. Subjects should not mark a cross on the actual horizontal line, nor should the line be measured to obtain a value.

VAS Score (Scale is 0 to 10)	Meaning
0	No pruritus
>0 but <4	Mild pruritus
>4 but <7	Moderate pruritus
>7 but <9	Severe pruritus
>9	Very severe pruritus

Table 6	Pruritus VAS	Assessment	[66]
		Assessment	

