## APPENDIX E: PBC-40 QUESTIONNAIRE

Protocol No.: GSN000300 Protocol Version No.: Final 4.0; Amendment 3 Protocol Date: 24 July 2018 Compound No.: GKT137831 Sponsor: Genkyotex Author: Cmed Clinical Services

P	a	ti	e	n	t	Ι	D

For each statement, please circle the response that comes closest to how you feel. If any of the statements do not apply to you please circle 'does not apply'.

Can you say how often the following statements about digestion and diet applied to you IN THE LAST FOUR WEEKS?

1	I was able to eat what I liked	Never	Rarely	Sometimes	Most of the time	Always	
2	I ate or drank only a small amount, and still felt bloated	Never	Rarely	Sometimes	Most of the time	Always	Did not
3	I felt unwell when I drank alcohol	Never	Rarely	Sometimes	Most of the time	Always	apply /never drink alcohol

And IN THE LAST FOUR WEEKS, how often did you experience any of the following?

4	I had discomfort in my right side	Never	Rarely	Sometimes	Most of the time	Always
5	I had dry eyes	Never	Rarely	Sometimes	Most of the time	Always
6	My mouth was very dry	Never	Rarely	Sometimes	Most of the time	Always
7	I had aches in the long bones of my arms and legs	Never	Rarely	Sometimes	Most of the time	Always

Some people with PBC experience itching. How often did you experience itching IN THE LAST FOUR WEEKS? If you did not itch, please circle 'does not apply'

8	Itching disturbed my sleep	Never	Rarely	Sometimes	Most of the time	Always	Did not apply/ no itch
9	I scratched so much I made my skin raw	Never	Rarely	Sometimes	Most of the time	Always	Did not apply/no itch
10	I felt embarrassed because of the itching	Never	Rarely	Sometimes	Most of the time	Always	Did not apply/no itch

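### Rifampicin and naltrexone have no stop date before Day 1, so the baseline PBC-40 itch recall can be on an antipruritic while Weeks 12 and 24 are off it

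*Protocol*

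**What the plan says.** Protocol 6.6.2 has two regimes. Lists (a) to (c) are barred for three months before Screening and throughout treatment. Lists (d) to (g) follow under a narrower rule: "In addition, the following medications are prohibited during the double-blind treatment period". List (g) reads in part "Pruritus medication: rifampicin, naltrexone. Anti-histamines are permitted, if the dose is stable for at least 8 weeks before Screening (Visit 1".

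The matching exclusion criterion, number 11 in Protocol 5.3, covers "Subjects receiving prohibited medications within 3 months of Screening (Visit 1) according to the list (a, b and c) provided in Section 6.6.2". List (g) is not in it. The Protocol Summary places the start of double-blind treatment at baseline/Day 1.

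Itch drugs that may continue do have a lead-in. Anti-histamines need eight weeks at a constant dose before Screening (list (g)). For colestyramine, Protocol 5.2 says "Subjects being treated for pruritus with colestyramine must be on a stable dose of colestyramine for at least 8 weeks prior to baseline/Day 1".

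Itch is measured in two ways, on Day 1 and at Weeks 12 and 24. The purpose of the VAS is stated in Protocol 8.1.6: "To capture the intensity of itching within the 24 hours preceding these visits". The PBC-40 itch block in Appendix E asks: "Some people with PBC experience itching. How often did you experience itching IN THE LAST FOUR WEEKS". SAP 6.5 takes the last value on or before first dose as baseline. SAP 8.7.2 gives descriptive summaries of the PBC-40 domains and the VAS, with no model. Both appear in the Top Line tables (SAP Appendix 1, items 28 and 29).

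**The concern.** A change from baseline is easiest to read when background treatment is the same at both ends. Here a subject may take an antipruritic during the period that the baseline questionnaire covers, and must be without it during the periods that the Week 12 and Week 24 questionnaires cover. If the drug was controlling itch, that subject's change score contains the effect of stopping it, and the arm's mean change moves towards worsening for a reason unrelated to study treatment.

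What is at stake is the reading of within-arm itch change. It is a listed secondary endpoint. The protocol also treats itch as relevant to a product's profile: section 2.1.3 is preceded by background text noting that a licensed competitor makes itch worse. With no model planned, readers will see the raw within-arm changes, and those are the quantities affected.

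**Working it through.** The plan states no figure on this point, so there is none to reproduce. The check is whether any rule forces an earlier stop, and then how the recall windows line up with the permitted stop dates.

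**Is there an earlier stop rule?**
- Protocol 6.6.2, list (g): barred during double-blind treatment only.
- Protocol 5.3, exclusion 11: lists (a), (b) and (c) only.
- Protocol 5.3, exclusion 20: investigator judgement, with no interval.
- Protocol 8.1.1: "Assessment of eligibility at Visits 1 and 2 should include a review of permitted and prohibited medications (see Section 6.6". This refers back to 6.6 and adds no interval of its own.
- The note at the head of 6.6.2 that the lists are not exhaustive can add drugs; it does not add a washout.

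None of these sets a date before Day 1.

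**Baseline PBC-40 itch (28-day recall).** Share of recall on drug = (28 - days off drug before Day 1) / 28.

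| Stop | Days off | Share of recall on drug |
|---|---|---|
| Day 1 | 0 | 28/28 = 100% |
| Day -7 | 7 | 21/28 = 75% |
| Day -14 | 14 | 14/28 = 50% |
| Day -21 | 21 | 7/28 = 25% |
| Day -28 | 28 | 0/28 = 0% |

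SAP 6.6, Table 1 puts Visit 1 at Day -28 to -7. A user who stops at Visit 1 therefore still has 0% to 75% of the baseline recall on drug.

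**Baseline VAS (24-hour recall).** It is on drug only after a stop on Day 1 or the day before. A stop at Visit 1 leaves it clear.

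**Weeks 12 and 24.** The visit tolerance is 3 days. The earliest Week 12 recall begins 84 - 3 - 28 = 53 days after first dose, and the earliest Week 24 recall begins 168 - 3 - 28 = 137 days after it. Under the wider SAP 6.4 windows these become 64 - 28 = 36 and 148 - 28 = 120 days. All lie inside the treatment period, so a compliant subject has no on-drug days in either recall.

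These shares count recall days only. Any effect that outlasts the final dose is left out, because the documents do not give its duration.

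**The case against.** **Sites may stop the drug at Visit 1.** The Protocol 8.1.1 medication review is part of eligibility and cites all of 6.6, so a site could treat current list (g) use at Visit 1 as something to stop then. That is a reasonable practice, and it would clear the VAS. It is not what the rule says, because the text it refers to bars list (g) only from Day 1. Even under this reading up to 75% of the PBC-40 recall can be on drug.

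**The comparison with colestyramine and anti-histamines is imperfect.** Those drugs continue, so they need a stability rule; list (g) drugs are withdrawn. Lists (d) to (f) have no washout either. This stands: the contrast shows that the protocol attends to itch co-medication, not that it contradicts itself. For a drug that must be withdrawn, the counterpart of a stability rule is a stop date that clears the baseline recall.

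**Off drug at Weeks 12 and 24 assumes compliance.** Correct. Use of a list (g) drug is not among the mandatory withdrawal reasons in Protocol 5.6.4.

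**No stated conclusion changes.** Randomization spreads these subjects over the arms, placebo is shown alongside, and SAP 8.7.2 already urges caution with unpowered secondary endpoints. SAP 8.5 summarizes and lists medications, so the subjects are visible. All of this limits the point, but no planned itch summary leaves those subjects out.

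**A reader might infer a definite shift in VAS scores.** Assuming, for instance, that 1% to 10% of subjects stop on Day 1 and then rise by 2 to 4 points gives arm-mean shifts of 0.01 x 2 = 0.02 to 0.10 x 4 = 0.40. The arithmetic is right, but neither input is in the documents. It also applies to the less exposed measure and supposes that every user stops at the last moment. These figures should not be relied on.

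**Conclusion.** The gap is real and narrow. The protocol lets a compliant user of rifampicin or naltrexone stop as late as Day 1. Any stop in the preceding 28 days leaves between 0% and 100% of the baseline PBC-40 itch recall on drug, depending on the date; the VAS is affected by recall only at the very end of that range. For compliant subjects the later assessments are off drug, so the within-arm change includes withdrawal.

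The size on the score scales cannot be stated, because use of these drugs and rebound after stopping are both unknown. There may be no such subject in the trial.

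A reader might also infer bias between arms or a problem with the main result. The documents support neither. Stopping is governed by the same rule in all three arms, so the effect is non-differential in expectation and only ordinary chance imbalance remains. The point concerns descriptive itch endpoints and gives no ground to doubt the primary GGT analysis. It is a cheap improvement, not a threat to the trial's conclusion.

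**What to change.** In 6.6.2(g) and in the exclusion criteria, require the last dose of rifampicin or naltrexone to be at least 28 days before Day 1. That clears the longer of the two recall windows.

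For subjects already enrolled, derive one flag: a list (g) drug with an end date on Day 1 or in the 28 days before it. Use raw end dates, and flag any partial end date that could fall in that interval. SAP 6.3 imputes a partial end date to the end of the month (or study discontinuation if sooner), which can carry a drug stopped before Day 1 past it. Report the number flagged per arm, and repeat the PBC-40 itch and pruritus VAS summaries without them. The flag rests on medication dates up to Day 1 and not on response, so applying it to all arms keeps the comparison fair. If nobody is flagged, one sentence in the report settles the matter.

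The cost is one clause, one criterion, one derived variable and one repeated set of summaries on data already collected. The downside is for patients: a few candidates spend up to four more weeks without an antipruritic before dosing. Consent is taken at Visit 1, so a user who stops there needs the full four-week screening window or cannot enter.
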